8.1.9. Unscheduled Visits

Unscheduled visits will occur when necessary, in the opinion of the PI or designee, to follow-up on an AE or abnormal laboratory test result between scheduled visits. Additionally, participants who report a potential autoimmune-related condition at any of the safety follow-up phone calls

will be requested to return to the clinic for an unscheduled visit to provide a blood sample for auto-antibody testing.

Unscheduled visits occurring before Day 64 will include a symptom-directed PE, measurement of vitals, AE (includes SAE/AESI) assessment inclusive of blood draw(s) for auto-antibody and/or TSH testing (if applicable), reviewing the status of ongoing AEs since the prior visit, updating of medication usage since the last visit, and (if applicable) review of e-diary data since the last visit.

Unscheduled visits occurring after Day 64 will include an AE/SAE/AESI assessment including blood draw(s) for auto-antibody and/or TSH testing if applicable and updating of medication usage since the last visit/contact (if AE/SAE/AESI-related). Other evaluations performed by the PI or designee during the unscheduled visit as part of the participant's medical care (eg, vital signs, symptom-directed PE, etc) and recommendations given to the participant (eg, referral to the participant's personal physician or specialist for further diagnosis and/or care, prescribed medications) will be documented in the participant's medical chart at the site. In the event of any referrals for further medical care, the PI or designee will follow up with the participant and/or personal physician/specialist to ensure the reporting of any SAEs or potential AESIs per the protocol (refer to [Section 9.3](#)).

8.2. Immunogenicity/Efficacy Assessments

8.2.1. Immunogenicity Testing

Blood samples (sera) for determination of TNA titers will be collected on Day 1 and Day 29 prior to vaccination, and on Day 64. Blood samples will be collected at EWV only if it falls within the visit window for Day 64.

All immunogenicity laboratory samples will be evaluated using a TNA assay. Specific procedures related to collection, processing storage, and shipment of the samples will be provided in the Laboratory Manual.

The TNA assay being used in this trial has been validated by Battelle Memorial Institute (Columbus, Ohio) under National Institute of Allergy and Infectious Diseases sponsorship {[Clement, 2008](#)}. The assay measures the functional ability of antisera containing anti-PA antibodies to specifically protect cells against *B. anthracis* lethal toxin cytotoxicity {[Stinson et al, 2005](#); [Li et al., 2008](#)}. The TNA assay results will be reported as the reciprocal of a serum sample dilution that results in 50% neutralization of lethal toxin cytotoxicity (50% effective dilution; ED₅₀). To standardize assay results, the results are divided by the ED₅₀ of a serum reference standard, and the resulting ratio is reported as a 50% neutralization factor, NF₅₀. Reference standard AVR801 will be used.

8.3. Safety Assessments

8.3.1. Adverse Events

Refer to [Section 9](#), Reporting Adverse Events.

8.3.2. Clinical Laboratory Tests

All analytes to be tested during screening/safety clinical laboratory tests are specified in [Table 7](#). Instructions for the collection, processing, storage, and shipment of screening and safety clinical laboratory test samples are provided separately in the Laboratory Manual. All samples will be sent to the central laboratory for analysis, except urine for pregnancy testing in WOCBP, which will be performed at the site and results documented in the eCRF.

It is the responsibility of the PI or designee to review the results of all screening and safety laboratory tests (including unscheduled lab tests) as they become available, initially for the assessment of study eligibility (screening laboratory test results, if not otherwise specified in the inclusion/exclusion criteria, should be within the central laboratory's reference ranges, or, if outside such ranges, be assessed by the investigator as not clinically significant) and subsequently for the continuous safety monitoring of participants. Review of the laboratory report must be documented.

The following assessments will be performed at Screening only:

- Urine drug screen (refer to [Table 7](#) for analytes)
- Serologic testing (HIV-1/HIV-2 antibodies, HBV surface antigen, and HCV antibody). Confirmatory testing will be performed on any samples that test positive for either HIV or HCV; no additional blood/serum will be required for this confirmatory testing.
- FSH test to confirm postmenopausal status in women having > 12 consecutive months without menses (refer to [Section 5.1](#)).

Pregnancy testing will be performed at all visits including EWV. Female participants who are confirmed at Screening to be surgically sterile (refer to [Section 5.1](#)) are exempt from pregnancy testing. A serum pregnancy test is required at Screening for all other female participants, including those suspected to be postmenopausal; any such individuals who are confirmed to be postmenopausal after the Screening FSH test result is known (refer to [Section 5.1](#)) are exempted from further pregnancy testing. Postscreening pregnancy testing in WOCBP (only) will consist of a urine pregnancy test at all visits except for a serum pregnancy test performed at Day 64 and the (if applicable) EWV. All urine pregnancy tests must be performed at the investigational site and documented to be negative on vaccination days before administration of vaccine. For participants with positive urine test results, a confirmatory serum pregnancy test will be performed. Vaccination will not be administered to any participant who tests positive for pregnancy.

Blood and urine samples for safety clinical laboratory testing (hematology, serum chemistry, urinalysis) will be collected at Screening and Day 29 and also at the EWV if the EWV occurs before Day 29. Refer to [Table 7](#) for the complete list of analytes to be tested. Blood samples for auto-antibody assessment of RF, ANA and anti-dsDNA antibodies and TSH will be taken at Day 1 prior to vaccination, Day 64/EWV, and at the time of unscheduled visit(s) if warranted from participant report(s) of potential AESI(s) at the safety follow-up phone call(s).

Clinical laboratory results for the lab analytes that appear in [Table 9](#) will be assigned by the central laboratory a toxicity grade (Grade 1=mild through Grade 4=potentially life-threatening)

according to the FDA Guidance for Industry: *Toxicity Grading Scale for Healthy Adult and Adolescent Volunteers Enrolled in Preventive Vaccine Clinical Trials* {[CBER, 2007](#)}. This grading – assessing severity – will aid the PI or designee in the evaluation of laboratory abnormalities and their reporting, if applicable, as AEs.

For each abnormal laboratory test result, the PI or designee needs to ascertain if this is a clinically significant change from baseline for that individual. This determination, however, does not necessarily need to be made the first time an abnormal value is observed. The PI or designee may repeat the laboratory test and/or request additional tests to verify the results of the original laboratory tests. The PI (or designee) will inform the MM of any unscheduled clinical laboratory testing, including but not limited to confirmatory testing of laboratory samples, with the exception that notification is not required for confirmatory testing for pregnancy, HCV, and HIV. Investigational sites will be alerted by the central laboratory of any Grade 3 or higher laboratory abnormalities. For any Grade 3 or higher laboratory result, the test will be repeated as soon as possible by the central lab to confirm the result. The PI or designee may request the participant return to the clinic for an unscheduled visit for an assessment of clinical status. The decision to redraw laboratory tests will be made by the PI (with notification to the MM) and/or MM and will be based on the type and severity of the laboratory abnormality and the clinical status of the participant. Any Grade 3 or higher neutropenia or lymphopenia must be evaluated with an unscheduled repeat complete blood count (CBC) approximately 72 hours after the initial specimen was drawn, unless a protocol-scheduled CBC has already shown resolution to Grade 1 or lesser toxicity.

If the original (retested sample) or repeat laboratory value is Grade 3 or higher, this will be considered an AE and will be recorded by the PI on the AE eCRF. Any other clinical laboratory abnormalities must also be reported as AEs if considered by the PI or designee to be a clinically significant change from baseline. As toxicity grading is being used in this study to evaluate and record AE severity (refer to [Section 9.2.1](#)), the lab toxicity grade is to be assigned as the AE toxicity grade when reporting on the AE eCRF. If the lab analyte does not have toxicity grading criteria specified in [Table 9](#), then the PI or designee will use the grading criteria for “illness or clinical AE” in [Table 8](#) to assign the AE toxicity grading. If an abnormal laboratory test result is a sign of a disease or syndrome, the disease or syndrome will be recorded as the AE/SAE and not the abnormal laboratory result. Clinical laboratory abnormalities may trigger study halting rules (see [Section 7.1](#)) and will require discontinuation of vaccinations in an individual participant if considered associated with vaccination (see [Section 7.3](#)).

Table 7: Screening/Safety Clinical Laboratory Tests

Hematology -Basophils -Eosinophils -Hematocrit -Hemoglobin -Lymphocytes -Monocytes -Neutrophils -Platelets -RBC count -WBC count Serum Chemistry -ALP -ALT -AST -Bilirubin, Total -BUN -Creatinine -Glucose, nonfasting	Urinalysis -Appearance -Bilirubin -Color -Glucose -Ketones -Leukocyte esterase -Nitrite -Occult blood -pH -Protein -Specific gravity -Urobilinogen -Microscopic examination (only if protein, nitrite, leukocyte esterase, or occult blood results are positive) Additional Tests -FSH (only in women having > 12 consecutive months without menses to confirm postmenopausal status) -Serum/urine pregnancy test (WOCBP only; also suspected postmenopausal women at Screening only) -TSH	Viral Serology: -anti-HCV antibody -anti-HIV antibody -HBsAg Urine Drug Screen: -Amphetamines -Barbiturates -Benzodiazepines -Cannabinoids -Cocaine -Opioids Autoantibodies -RF -ANA -anti-dsDNA antibodies
---	---	--

ALP=alkaline phosphatase; ALT=alanine transaminase; ANA=antinuclear antibody; AST=aspartate transaminase; BUN=blood urea nitrogen; dsDNA=double stranded deoxyribonucleic acid; FSH=follicle-stimulating hormone; HBsAg=hepatitis B surface antigen; HCV= hepatitis C virus; HIV=human immunodeficiency virus; RBC=red blood cell; RF=rheumatoid factor; TSH=thyroid-stimulating hormone; WBC=white blood cell; WOCBP=woman of childbearing potential.

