Medication usage	X	X	X	X	X	X	X	X	Medications taken within 30 days prior to the Screening visit or since the last visit (including unscheduled visit) through Day 64/EWV will be recorded. Additionally, medication use will be recorded at the time of the safety follow-up phone calls (also during unscheduled visits following safety phone calls) only for those subjects who report an AE, SAE or AESI.

Study Periods	Screening	In-clinic Visits					Safety Follow-up Phone Calls	Unscheduled Visit	Comments
		1	15 (±1)	29 (±2)	64 (±3)	EWV			
Study Day (Visit Window in Days)	-28 to -2						43 (±2), 120 (±14), 211 (±14), 302 (±14), 394 (±14)	-	On unscheduled visit days: X _{<D64} = assessment to be performed only if before Day 64.
Complete PE	X				X	X			Abnormal findings are to be recorded as AEs after Day 1 postvaccination if new or increased in severity unless the PE abnormality is part of a symptom complex that is already reported as an AE.
Viral serology testing	X								Testing for HIV-1 or HIV-2 antibodies, hepatitis B surface antigen, and hepatitis C antibody.
Use of adequate method of contraception (WOCBP only)	X	X	X	X	X	X	X	X	The preferred method of adequate contraception as defined in Section 5.2 will be documented in the WOCBP's chart and reviewed for continued use at every visit or contact thereafter.
FSH	X								Performed to confirm postmenopausal status only in women having >12 consecutive months without menses.
Hematology	X			X		X			Any Grade 3 neutropenia or lymphopenia will be evaluated with an unscheduled repeat CBC approximately 72 hours after the initial specimen was drawn, unless a protocol-scheduled CBC has already shown resolution to Grade 1 or lesser toxicity. EWV will include hematology testing only if the visit occurs before Day 29.
Serum chemistry	X			X		X			EWV will include serum chemistry testing only if the visit occurs before Day 29.

Study Periods	Screening	In-clinic Visits					Safety Follow-up Phone Calls	Unscheduled Visit	Comments
		1	15 (±1)	29 (±2)	64 (±3)	EWV			
Study Day (Visit Window in Days)	-28 to -2						43 (±2), 120 (±14), 211 (±14), 302 (±14), 394 (±14)	-	On unscheduled visit days: X<D64 = assessment to be performed only if before Day 64.
Urinalysis	X			X		X			EWV will include urinalysis testing only if the visit occurs before Day 29.
Urine drug screening	X								Participants with any positive test result may not be randomized.

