8.3.4. Vital Signs

Vital signs including systolic and diastolic blood pressure (sitting), heart rate, respiration rate, and temperature will be obtained at Screening and each subsequent clinic visit through Day 64/EWV, including unscheduled visits occurring before Day 64. Height and weight will only be recorded at Screening. On vaccination days (Days 1, 15, and 29), vital signs will be assessed prior to vaccination and at 30 ± 5 minutes postvaccination.

The PI or designee will assess vital sign results against toxicity grade criteria (Grade 1=mild through Grade 4=potentially life-threatening) according to the FDA Guidance for Industry: *Toxicity Grading Scale for Healthy Adult and Adolescent Volunteers Enrolled in Preventive Vaccine Clinical Trials* {[CBER, 2007](#)} – refer to [Table 8](#), with grading for oral temperature (fever), heart rate (tachycardia, bradycardia), blood pressure (hypertension, hypotension), and respiratory rate. This grading – assessing severity – will aid in the evaluation of abnormalities and their reporting, if applicable, as AEs.

Any vital sign abnormalities may be followed up with repeat testing. Grade 3 or higher vital signs will be repeated twice to verify that the severity is a Grade 3 or higher. If two of the three assessments are Grade 3 or higher, the vital sign will be reported as a Grade 3 or higher abnormality. All Grade 3 or higher vital sign abnormalities and those vital sign abnormalities determined by the PI or designee to be a clinically significant change from baseline for that participant will be recorded as AEs. As toxicity grading is being used in this study to evaluate and record AE severity (refer to [Section 9.2.1](#)), the vital sign toxicity grade is to be assigned as the AE toxicity grade when reporting on the AE eCRF. Vital sign abnormalities are not to be separately reported as AEs if the abnormality is part of a symptom complex that is already reported as an AE. Vital sign abnormalities may trigger individual participant or study halting rules (refer to [Section 7](#)).

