9.2. Eliciting and Reporting Adverse Events

AEs (including SAEs and potential AESIs) reported spontaneously by the participant and/or in response to an open question from the PI or designee or revealed by observation (eg, during PE or from a clinical test result) will be recorded by the PI or designee on the AE eCRF if they

occurred from the time of the first vaccination on Day 1 up to Month 13, regardless of causal association with the IP. AE reporting is required for any new observation presenting after the first vaccination or for a deterioration of baseline condition (eg, increased severity/frequency). From the signing of the ICF until immediately before the first vaccination on Day 1, only AEs resulting from a study-related procedure will be recorded on the AE eCRF; all other events reported in this time period will be recorded as signs and symptoms on the Medical History eCRF. If there is any doubt as to whether a clinical or laboratory observation is an AE, the event will be considered an AE and recorded on the AE eCRF.

Refer to the specific sections on clinical laboratory tests ([Section 8.3.2](#)), PEs ([Section 8.3.3](#)), vital signs ([Section 8.3.4](#)), and e-diary reactogenicity ([Section 8.3.5.1](#)) for details on AE reporting based on participant observation and clinical test results.

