7.2.1 Overall Summary of TEAEs

A treatment-emergent adverse event (TEAE) is defined as an AE that presents after the initiation of treatment or any AEs already present that worsen in either intensity or frequency following treatment. For programming purpose, any AEs with start date on or after the start date of the first vaccination will be counted as treatment-emergent. AEs with missing start dates, but with end dates later than the date of first vaccination will also be counted as treatment emergent.

An overall summary table with the following TEAE categories will be provided:

- TEAEs
- Vaccine-related TEAEs
- Grade 3 or 4 TEAEs
- Vaccine-related Grade 3 or higher TEAEs
- Serious TEAEs
- Serious vaccine-related TEAEs
- Death
- TEAEs leading to discontinuation of vaccination
- TEAEs leading to study withdrawal
- AESIs
- Vaccine-related AESIs

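### Confirmed Grade 3+ laboratory and vital-sign values become AEs without reference to baseline, and the SAP's date-only rule then counts unchanged values as Grade 3 TEAEs

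*Protocol*

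**What the plan says.** **Laboratory values (Protocol 8.3.2).** A Grade 3+ value is retested or repeated. Then: "If the original (retested sample) or repeat laboratory value is Grade 3 or higher, this will be considered an AE". Such a value goes on the AE form. The comparison with baseline governs only the remaining abnormalities: "Any other clinical laboratory abnormalities must also be reported as AEs if considered by the PI or designee to be a clinically significant change"; the reference point is the participant's baseline value. Where the value is a sign of an illness, "the disease or syndrome will be recorded as the AE/SAE and not the abnormal laboratory result".

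**Vital signs (Protocol 8.3.4).** Grade 3+ has to be confirmed by two of three readings. Two classes then go on the AE form: "All Grade 3 or higher vital sign abnormalities and those vital sign abnormalities determined by the PI or designee" to have changed from baseline to a clinically significant degree. Change from baseline is a second way in, not a condition on the first. Abnormalities that belong to a symptom complex already reported are not reported again.

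**General reporting rule (Protocol 9.2).** "AE reporting is required for any new observation presenting after the first vaccination or for a deterioration of baseline condition". Before the first vaccination only procedure-related events are recorded as AEs; other findings go to medical history.

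**Physical examination (Protocol Table 6 and 8.3.3).** "Abnormal findings are to be recorded as AEs after Day 1 postvaccination if new or increased in severity".

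**Treatment emergence (Protocol 10.6.2, SAP 7.2.1).** An event already present is a TEAE only if it worsens in intensity or frequency. For programming, however, "any AEs with start date on or after the start date of the first vaccination will be counted as treatment-emergent".

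**The concern.** Three rules for the same kind of finding do not line up. A confirmed Grade 3 laboratory or vital-sign value has to be recorded even if it was at the same grade before vaccination. The 9.2 reporting rule and the physical-examination rule would not call for that. The SAP definition of a TEAE would screen such a record out, but its programming rule does not, because it looks only at the start date.

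At stake are the Grade 3 and 4 TEAE line in the overall summary, the tables by severity, and the Grade 3 or 4 TEAE listing. These would mix new findings with long-standing ones. The records are also candidates for the study-level criterion in Protocol 7.1 (more than 3% of participants with the same AE at Grade 3 or above), which is not restricted to treatment-emergent or related events.

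**Working it through.** The documents state no figure to reproduce, so the check is mainly a reading of the rules in sequence.

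**1. Can a participant with a Grade 3 baseline value be enrolled?** Yes. Protocol 5.4 admits out-of-range screening laboratory values that the investigator judges not clinically significant. The criteria in 5.1 and 5.2 set no numerical limit on blood pressure. On the Appendix A scale, Grade 3 starts above 155 mmHg systolic or above 100 mmHg diastolic, and at 2+ urine protein.

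**2. Is the unchanged value recorded as an AE?** Yes, once confirmed, under 8.3.2 or 8.3.4. After the first vaccination, safety laboratories have one scheduled visit (Day 29, or an early withdrawal visit before it). Vital signs have six scheduled readings: Day 1 after the injection, before and after on Days 15 and 29, and Day 64. The haemoglobin-decrease items in Table 9 are already graded on change from baseline and are not at issue.

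**3. Is it flagged as treatment-emergent?** That depends on its start date. If dated at the post-vaccination visit, yes. If the start date is missing, SAP 4.4 imputes the first vaccination date, so again yes unless a known earlier end date replaces it. If dated before vaccination, no. The documents do not say how onset is dated for a finding already present at baseline.

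**4. Does the definition agree?** No. An event already present and not worse is outside the TEAE definition. The gap is between that definition and the SAP's own programming rule.

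**5. Illustration of size.** Let *b* be the proportion with an unchanged Grade 3 value recorded with a post-vaccination date. The documents give no value, so every *b* below is assumed. Added participants = 3300*b* and 550*b*. For the ratio, assume true new rates for one item of 1.0% (AV7909) and 0.5% (BioThrax), so the true ratio is 2.0 and the true difference is 0.5 points. For one item, a person already at Grade 3 cannot also be a new Grade 3 case, so the rates add:

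| *b* | Added, AV7909 | Added, BioThrax | Tabulated rates | Ratio | Difference |
|---|---|---|---|---|---|
| 0.5% | 16.5 | 2.75 | 1.5% vs 1.0% | 1.50 | 0.5 points |
| 1.0% | 33 | 5.5 | 2.0% vs 1.5% | 1.33 | 0.5 points |
| 1.5% | 49.5 | 8.25 | 2.5% vs 2.0% | 1.25 | 0.5 points |
| 2.0% | 66 | 11 | 3.0% vs 2.5% | 1.20 | 0.5 points |

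Randomization makes *b* equal in expectation across arms, so rates rise in both, the ratio shrinks and the difference stays. In a table of any Grade 3 TEAE a person can have both kinds of event. If these are independent, the difference is multiplied by 1 − *b*: at 2%, 0.5 × 0.98 = 0.49 points, which is negligible.

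**6. The 3% criterion.** 0.03 × 500 = 15, so at least 16 participants at the planned review of the first 500; 0.03 × 3850 = 115.5, so at least 116 in the full sample. Unchanged baseline findings would count toward these totals if the criterion is applied to all recorded AEs.

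**The case against.** The case for leaving the plan alone has real force.

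- **The AE definition is not breached.** A reader might infer that the Grade 3 rule contradicts the definition of an AE. It does not: Protocol 9.1.1 gives an abnormal laboratory finding as an example and sets no new-or-worse test. Nor can a recording rule contradict the TEAE definition, which only classifies what has been recorded.
- **The conflict with 9.2 is soft.** That section says when reporting is required, not when it is forbidden. It sends the reader to 8.3.2 and 8.3.4 for detail and treats doubtful observations as AEs. One can read a general rule with deliberately wider specific rules. This stands as a reason not to shrink the AE form. It does not explain why physical findings carry a baseline condition and these do not, and an unchanged documented grade is not a doubtful case.
- **The net is narrower than every Grade 3 value.** Confirmation is required, the carve-outs apply, and participants must be healthy by history and examination. This stands, and probably keeps the number small.
- **Readers can already separate old from new.** Shift tables by toxicity grade are planned for laboratory data (SAP 7.3) and vital signs (SAP 7.4). That is true, but they do not correct the TEAE tables.
- **No formal comparison is affected.** Relative risks are planned only for serious TEAEs and AESIs, without hypothesis tests. Grade 3 TEAEs are tabulated only. This also stands.

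**Conclusion.** The point holds as a mismatch between recording, definition and programming. Followed as written, the plan tabulates a confirmed Grade 3+ laboratory or vital-sign value that has not changed since baseline as a Grade 3 TEAE whenever its AE is dated at a post-vaccination visit. Absolute Grade 3 TEAE rates are inflated in both arms and ratios between arms are pulled toward 1.

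The size cannot be derived from the documents. Phase 2 saw Grade 3+ values for several analytes (Protocol 2.2.3), but the text does not say whether they were present before vaccination. The illustration rests entirely on assumed rates.

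A reader might also infer that the AV7909–BioThrax comparison is biased in favour of one arm, that the primary safety endpoint is affected, or that the trial would be halted by background findings. The documents support none of these. The expected inflation is the same in both arms, the risk difference is not biased in expectation, and unchanged values of this kind do not become SAEs merely by being graded 3. Under Protocol 7.1 enrollment and vaccination may be halted pending review; a halt is not automatic.

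**What to change.** 1. **Protocol 8.3.2 and 8.3.4 against 9.2.** Reconcile them, and say how onset is dated for a finding already present at baseline. This need not remove records from the AE form. Removing them would lose automatic capture of worsening within open-ended Grade 3 categories, such as systolic pressure above 155 mmHg. It would also change what reaches the DSMB Chair.
2. **SAP 7.2.1.** For AEs that arise from a laboratory or vital-sign value, compare the AE grade with the baseline grade, using the baseline in SAP 3.4. Do not count as treatment-emergent those with no increase in grade and no investigator-judged clinically significant worsening. Alternatively, present the Grade 3+ TEAE tables with and without them. The second option is safer if that judgement is not held as a data item; the documents describe no field for it. Keep all such records in the AE listings and shift tables.
3. **Protocol 7.1.** State consistently whether these AEs count toward the 3% criterion. No halting rule is proposed here.

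The cost is a few sentences and one derived flag. The flag has to merge baseline grades from the central laboratory, whose data are held outside the EDC (Protocol 11.3), and from vital signs with the AE records. The Grade 3 TEAE tables would show slightly fewer events.
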